Alcohol use is inextricably linked to the HIV epidemic in fishing communities on Lake Victoria in Uganda, where HIV incidence among regular drinkers is 5 times higher than among non-drinkers.¹ Fishing communities are an HIV “hotspot;” HIV prevalence in fishing communities is estimated at >25%²⁻⁴ compared to the national prevalence of 7.3%.⁵ Prevalent alcohol consumption is also consistently reported across a range of studies with fisherfolk in Uganda^{3, 4, 6-8} and hazardous and harmful alcohol use, especially among *fisherfolk men*, is dramatically more prevalent (37%)⁶ than in the general population (5.8%).⁹ In our preliminary research Among the 61% of men who reported alcohol use, 60.2% had AUDIT scores (>7) indicative of hazardous/harmful alcohol use and 16% had AUDIT scores (>16) indicative of a high level of alcohol problems.⁶ Heavy alcohol use is especially problematic among individuals living with HIV as it leads to poor treatment outcomes¹⁰ and is associated with suboptimal antiretroviral (ART) adherence and engagement in care.¹¹⁻¹³

Like much of Uganda’s economy, fishing villages operate on a cash economy; workers get daily cash payments for their work but have limited mechanisms for savings due to a lack of access to traditional banking infrastructure. Poverty and stressful work conditions paired with easy access to alcohol and cash with no means of savings (i.e., access to banks, savings accounts) may be drivers of alcohol consumption among fisherfolk men.¹⁴ Moreover, frequent mobility and work responsibilities, a lack of social support, HIV stigma, and distance to the clinic have been shown to impede access to HIV care services among fisherfolk.^{15, 16} Given the unique context of heavy alcohol use and challenges with engaging fisherfolk men in HIV care, a combination intervention, which addresses structural as well as behavioral factors may be needed for this population.

We propose to develop and pilot a brief combination intervention called *Kisoboka* which addresses the key drivers of alcohol use and barriers to HIV care engagement and ART adherence in this population. We address these multi-level factors in an intervention which combines behavioral components to promote behavior change with a structural component which changes the mode of work payments from cash to *mobile money*, to reduce “cash in the pocket,” and increase the accessibility of savings through mobile phone-based banking services. For the behavioral components, we will combine and adapt two efficacious alcohol interventions to the cultural and situational context of this population: a brief Motivational Interviewing (MI)-based intervention tested in Kenya¹⁷ and an intervention rooted in behavioral economics.¹⁸ The latter intervention focuses on increasing the extent to which individuals’ behavior is motivated by and consistent with their long-term goals such as saving money for the future—in which we will interweave the structural component of the intervention.

2. Specific objectives

Objective 1. Use formative research with fisherfolk men living with HIV and community stakeholders to adapt and develop a behavioral intervention *Kisoboka* (“*It is possible!*”) to reduce heavy alcohol use and promote engagement in HIV care and ART adherence among fisherfolk men living with HIV.

Objective 1b. Further refine the intervention through an initial pilot test with 15 participants examining feasibility and acceptability.

Objective 2. Pilot the *Kisoboka* intervention, randomizing to the *Kisoboka* intervention arm (n=80) or to the control arm (n=80, alcohol screening and referral). We will assess feasibility, acceptability, and preliminary estimates of the potential for the intervention, as compared to control, to decrease heavy drinking frequency and improve HIV care engagement and ART adherence through 6-month follow-up among this key population.

3. Methodology

3.1 Setting and population.

Research setting. The study will be conducted in Wakiso District, Uganda which is on the northern side of Lake Victoria. Our team has conducted several studies in fishing communities in this district. Majority of residents of fishing villages work in the fishing industry and individuals receive daily cash payments for their work. The study will take place at 5 HIV clinics in Wakiso District which serve large populations of fisherfolk. *Fisherfolk* include fishermen, fish traders, fish processors, fish loaders, boat/fishing equipment repairmen, and other workers who engage in work supporting the fishing industry within the fishing communities. As of May 2018, there were over 1,700 adult male patients on ART at these clinics.

Study population. The study population is fisherfolk men aged 18-50 who engage in heavy alcohol use. The age range focuses on men who are the most high risk group for HIV and unhealthy alcohol use.^{5, 9}

Inclusion criteria: men aged 18-50; work as a fisherman, fish trader, fish processor, fish loader, related occupation supporting the fishing industry; living with HIV; on antiretroviral treatment for at least 1 month, report missing 1 or more dose of ART in the prior 2 weeks; **Alcohol use criteria:** consumed 5 or more drinks per occasion 2 or more times in the prior month or have an AUDIT-C (Alcohol Use Disorder Identification Test-Concise) score of ≥ 4 ¹⁹; not planning to move from the area within the next 6 weeks; have their own mobile phone and can be reached via phone (nearly all ($>97\%$) fisherfolk men have their own mobile phones and receive incoming calls is free).

Consuming ≥ 5 drinks per occasion is the definition of heavy episodic drinking or binge drinking, as defined the National Institutes of Alcohol Abuse and Alcoholism (NIAAA). This type of drinking is the most concerning type of alcohol use for individuals who are HIV positive. Recent longitudinal data has shown that greater frequency of heavy alcohol use is directly associated with poor ART adherence and an important clinical outcome (lower CD4 count) and is indirectly associated with higher HIV viral load (via lower adherence).¹⁰ Based on this evidence, we focus on heavy alcohol use for this intervention, and restrict our sample to those reporting recent heavy/binge alcohol use.

Exclusion criteria: visibly intoxicated at the time of enrollment (eligible to enroll when sober); does not speak Luganda or English; unable to read basic Luganda or English; currently receiving work payments via mobile money or currently uses mobile money savings services; occupation is a boat owner or engine owner.

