3.2 Study design and procedures

Intervention

Recruitment, eligibility screening, and informed consent.

We will recruit men who are patients at Mildmay's HIV clinics in Wakiso District using two methods.

- 1) After a male patient checks in for his appointment and his HIV clinic record is pulled, a clinic staff member will review the patient's records to determine if they may be potentially eligible (male, aged 18-50, on ART for at least 6 months, work in the fishing industry, can be reached by phone). After the patient has completed his clinic appointment, clinic staff will refer male patients who are potentially eligible to a research assistant for eligibility screening.
- 2) Clinic staff will also review clinic records to identify potentially eligible patients and will call the patient to tell him about the study. If the patient is interested, they will seek permission to share his phone number and name with the researchers, provide the contact number for the research assistant, and offer that the patient can come to the clinic to meet the research

assistant to learn more about the study. Study staff will briefly describe the study and seek informed consent to conduct eligibility screening.

Those determined eligible will be offered participation in the study and study staff will obtain written informed consent.

Intervention content and structure

After participants complete the baseline structured interview, the research assistant will refer them to the appropriate counselor who will provide intervention participants with the *KISOBOKA* ("It is possible!"). Our proposed brief intervention consists of 4 sessions: 2 individual, 2 group over 6 weeks, plus 2 times weekly text message reminders of life/savings (family prosperity, opportunities for children) and healthy living goals. Through these sessions the combination intervention will address environmental, interpersonal, and individual level factors which are key drivers of alcohol use and key barriers to HIV care engagement and adherence in this population.

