3.3 Data collection

Stage 1b randomized pilot intervention trial (n=160):

Baseline data collection. After the informed consent process in a one-on-one interview (~60 minutes) using a computerized structured questionnaire, the interviewer will collect demographic information and detailed contact information (e.g., phone numbers, contact details of individuals who would know how to find the participant) to facilitate participant retention, and a venous blood sample for the alcohol biomarker measure (PEth).

Interviewers will set the appointments for the 3- and 6-month follow-up.

3 and 6-month follow-up data collection. For participants' convenience the 3-month follow-up interview may be conducted by phone whereas the 6-month follow-up interview must be in person since it involves obtaining a venous blood sample. For the 6-month follow-up, study interviewers will conduct follow-up data collection either at the study office at the clinic or, if requested by the participant, by meeting at a location of the participant's choosing. In our prior work in Uganda, we have found that participants who may have challenges in coming to the study office prefer to have the interviewer come to them. At 3- and 6-month follow-up the interviewers will conduct an individual structured interviewer-administered computer-based interview (~45 minutes duration). At the 6-month follow-up they will also collect 2mls of venous blood for PEth testing. If participants cannot be reached for the blood sample, we will still conduct the interview over the phone. This will allow us to still obtain some 6-month follow-up data from all participants. However, we will continue to follow up with these participants to obtain the venous blood sample even after the phone interview. Follow-up interviewers will be blinded to study arm assignment.

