3.4 Measures

Unless otherwise noted all variables will be assessed at baseline and at follow-up, 3 and 6 months from baseline.

Primary alcohol outcome. We will use an **alcohol biomarker**: phosphatidylethanol (PEth) as the primary alcohol outcomes assessed at baseline and 6-month follow-up. PEth is a phospholipid which is formed only in the presence of alcohol and thus is highly specific.⁴⁷ PEth has shown good performance as a medium-term biomarker⁴⁸ and in controlled laboratory studies, correlated well with level of consumption (Spearman's $r = 0.6-0.8$).⁴⁹⁻⁵²

We will also use the AUDIT-C¹⁹ as another measure of hazardous alcohol use.

ART adherence: We will assess adherence to ART using the AIDS Clinical Trials Group Adherence measures (AACTG),⁵³ which includes recall questions about ARVs missed for the previous 4 days prior to the interview. It has demonstrated construct validity in Uganda and similar settings⁵⁴ and shows strong correlations with HIV VL⁵⁵ and moderate correlations with electronic adherence monitoring.⁵⁶

Measures and analysis for assessment of feasibility:

To inform a future larger randomized trial of the *KISOBOKA* intervention we follow Bowen et al.'s suggestions for conducting feasibility studies in preparation for larger RCTs²⁴ which includes assessing feasibility on the following dimensions: **acceptability, demand/use, implementation, and practicality**. We will document the number of intervention sessions participants attended which will speak to demand for/use of the intervention. To monitor implementation for the individual and group intervention sessions we will audio record intervention sessions and transcribe and code 20% of sessions to monitor intervention fidelity. Related to the practicality of the procedures, we will assess our retention rate through the 6-month follow-up to determine if we will need to develop additional retention procedures to maximize retention in a larger trial with a longer follow-up.

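### Relocation is screened for 6 weeks only, but follow-up PEth needs an in-person draw at 6 months; expected moves are not recorded, so foreseeable PEth loss cannot be identified or adjusted for

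*Combined protocol and SAP*

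**What the plan says.** The inclusion criteria in Section 3.1 contain one condition on residence: the man is "not planning to move from the area within the next 6 weeks". None of the exclusion criteria concerns relocation. Section 3.2 describes the intervention as "4 sessions: 2 individual, 2 group over 6 weeks", so the residence window and the session period coincide.

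The outcome schedule is longer. Section 3.4 describes PEth "as the primary alcohol outcomes assessed at baseline and 6-month follow-up", and the Statistical Analysis Plan in Section 3.5 confirms two PEth time points against three for the other variables. Section 3.3 states that "the 6-month follow-up interview must be in person since it involves obtaining a venous blood sample".

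Section 3.3 also gives safeguards. The interviewer can see the man "by meeting at a location of the participant's choosing". Contacts who could trace him are collected at baseline. "If participants cannot be reached for the blood sample, we will still conduct the interview over the phone", and staff keep trying for the blood sample after that call. The sample-size text in Section 3.2 allows for 25% attrition. Section 3.4 makes retention to 6 months a feasibility measure.

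**The concern.** The screen protects attendance at the sessions, not collection of the 6-month PEth value. PEth is the only biomarker among the three primary outcomes. It has no 3-month value to fall back on and cannot be collected by phone, as AUDIT-C and self-reported adherence can.

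The opening background section names "frequent mobility and work responsibilities" among the things that impede access to HIV care in this population. If men who move also differ in drinking or care engagement, their missing PEth is not a random subset. Two aims of the pilot are then affected: the PEth effect-size estimate intended for a later trial, and the 6-month retention rate used to decide whether that trial needs more retention procedures.

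**Working it through.** **1. Timing.** The screen covers 6 weeks and the PEth endpoint is at about 26 weeks. 6/26 = 23%, so about 20 weeks are not covered by any question on moving.

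**2. How a PEth value is lost.** A man who says at screening that he will leave in month 3 meets Section 3.1 as written. At month 6 he can be visited elsewhere, but Section 3.3 also requires the venous sample to reach a laboratory 6 to 10 hours after collection, which limits how far away he can be bled. If he cannot be bled, the phone interview gives AUDIT-C and adherence but no PEth. Section 3.3 describes no procedure specific to men who have left the area.

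**3. The plan's own allowance.** 160 × (1 − 0.25) = 120 men, or 60 per arm. The 95% confidence half-width for a difference in means is 1.96 × √(2/60) = 0.36 SD. (The illustrative 72% power is not used here. A plain two-sample calculation with d = 0.2, 60 per arm and an assumed two-sided 0.05 level gives 19%, but that is a separate matter.)

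**4. Loss from movers alone.** The documents give no relocation rate, so the fractions f below are assumptions, and every such man is assumed not to be bled. Men left = 160 × (1 − f). Standard error inflation against 160 = 1/√(1 − f) − 1.

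| f | Men with 6-month PEth | SE inflation |
|---|---|---|
| 5% | 152 | 2.6% |
| 10% | 144 | 5.4% |
| 20% | 128 | 11.8% |
| 25% (planned attrition, all causes) | 120 | 15.5% |

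The first three rows all stay above the planned 120. Precision falls below plan only if total loss exceeds 25%: at an assumed 30% there are 56 per arm (half-width 0.37 SD), and at 40% there are 48 per arm (0.40 SD).

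**5. Mixing in the completeness rate.** Suppose 120 of 160 men (75%) give a 6-month PEth value. If expected movers are lost no more often than others, the rate among men with no plan to move is also 75%. If all expected movers are lost, it is 120 divided by the number of other men:

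| Expected movers (assumed) | Other men | Completeness among other men |
|---|---|---|
| 8 (5%) | 152 | 120/152 = 79% |
| 16 (10%) | 144 | 120/144 = 83% |
| 32 (20%) | 128 | 120/128 = 94% |

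The same observed 75% could thus mean a wide range of retention among men who meant to stay. Without the baseline answer these cases cannot be told apart.

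**6. Analysis.** Section 3.5 names intent to treat and GEE but no method for missing data. Unweighted GEE generally needs missingness to be completely at random, apart from dependence on covariates in the model. The potential covariates in Section 3.2 include distance or time to the clinic but not expected relocation. The planned analysis therefore cannot adjust for it.

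**The case against.** The strongest reply is that the 6-week window is a coherent choice. It ensures that men can receive the sessions, and the trial is a pilot that states it is not powered and already allows 25% attrition. Off-site visits, tracing contacts and continued pursuit of the sample all reduce the loss. A screening question catches only moves already planned, and the background speaks of mobility, not of relocations known months ahead. A 6-month residence criterion would narrow a mobile population and could flatter the retention rate that the pilot wants to learn. The screen also applies equally to both arms.

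Most of this stands. A reader might infer that men who move are likely to have no 6-month PEth, or that the trial will end with fewer PEth values than planned. The documents support neither: there is no relocation rate, the safeguards are real, and losses of 5% to 20% from this cause alone fit within the allowance. A reader might also infer that the criterion must be extended to 6 months. That is a trade-off, not a correction.

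The objection does not answer the lack of a record. The safeguards reduce the loss but do not show who was expected to leave, and the attrition allowance covers the number lost, not whether the loss is informative.

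**Conclusion.** The mismatch is confirmed from the text: a 6-week relocation screen against a 6-month in-person PEth draw, with no exclusion or baseline item covering the roughly 20 weeks between. Men who already expect to leave can be enrolled and may give no follow-up PEth. No shortfall against the planned 120 of 160 is shown, and no bias between arms is demonstrated.

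The precision cost from this cause is modest: 2.6% to 11.8% on the standard error for assumed losses of 5% to 20%, measured from full follow-up. The more useful finding is that foreseeable, possibly informative PEth loss goes unrecorded and unadjusted, and is mixed into a feasibility rate that will guide the next trial. The size of that effect rests on assumed shares of movers. Whether the loss is informative is plausible from the background section but not established. This is a worthwhile, low-cost improvement rather than a flaw that undermines the design.

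**What to change.** Keep the 6-week criterion and make three additions.

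1. Ask every man at baseline whether he expects to move from the area before month 6. Ask before the study ID is issued, because under Section 3.2 the ID determines the arm.
2. Report 6-month PEth completeness and retention by that answer and by arm. Show the two separately, because a man reached only by phone has interview data but no PEth.
3. State a missing-data analysis for PEth in Section 3.5 that uses the answer as a predictor, for example multiple imputation or inverse-probability-weighted GEE.

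The cost is one question in an interview of about 60 minutes and a small amount of analysis. Nobody is excluded, and the answer cannot be recovered reliably later. Extending the residence criterion to 6 months remains an option for the sponsor to weigh: it would probably reduce PEth loss, but from a smaller and less mobile pool and with a retention rate that may look better than the target population would give.

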3.2 Study design and procedures

Intervention

Recruitment, eligibility screening, and informed consent.

We will recruit men who are patients at Mildmay's HIV clinics in Wakiso District using two methods.

- 1) After a male patient checks in for his appointment and his HIV clinic record is pulled, a clinic staff member will review the patient's records to determine if they may be potentially eligible (male, aged 18-50, on ART for at least 6 months, work in the fishing industry, can be reached by phone). After the patient has completed his clinic appointment, clinic staff will refer male patients who are potentially eligible to a research assistant for eligibility screening.
- 2) Clinic staff will also review clinic records to identify potentially eligible patients and will call the patient to tell him about the study. If the patient is interested, they will seek permission to share his phone number and name with the researchers, provide the contact number for the research assistant, and offer that the patient can come to the clinic to meet the research

assistant to learn more about the study. Study staff will briefly describe the study and seek informed consent to conduct eligibility screening.

Those determined eligible will be offered participation in the study and study staff will obtain written informed consent.

Intervention content and structure

After participants complete the baseline structured interview, the research assistant will refer them to the appropriate counselor who will provide intervention participants with the *KISOBOKA* ("It is possible!"). Our proposed brief intervention consists of 4 sessions: 2 individual, 2 group over 6 weeks, plus 2 times weekly text message reminders of life/savings (family prosperity, opportunities for children) and healthy living goals. Through these sessions the combination intervention will address environmental, interpersonal, and individual level factors which are key drivers of alcohol use and key barriers to HIV care engagement and adherence in this population.

Session 1, at enrollment, In-person individual session combining MI-based counseling and goal setting and setting up the structural component of the intervention. During session 1 the counselor will: (1) Set-up the participant to receive payments for work via mobile and (if necessary) helping the participant set up a free mobile money account; (2) discuss short and long term life and healthy living goals, financial planning and savings goal setting (e.g., % of income to reach target savings amount in X time), set goal to transfer X% of daily earnings to a savings account, establish a separate healthcare savings; (3) feedback about AUDIT-C score and assess barriers to HIV care engagement and adherence; (4) MI-based counseling about alcohol use and HIV care engagement and adherence to develop discrepancy between their behavior and savings/life and health goals, engage client in change talk including setting specific goals, discussing barriers, and ways to overcome barriers; (5) discuss alcohol-free leisure activities; (6) provide a diary for participant to track spending and savings and time and money spent drinking.

Session 2, 2 weeks after enrollment, MI-based individual session via phone. Counselors will call participants and will: (1) review progress on alcohol and HIV care engagement and adherence goals, additional counseling as needed to set new goals, overcome barriers or reinforce positive behaviors; (2) review spending and saving diary and progress on savings; (3) review participant's receipt of work payments via mobile money, progress on savings goals, and help troubleshoot any problems.

Sessions 3 and 4, approximately 4 and 6 weeks after enrollment, Group sessions with 4-8 participants per group. Each session will consist of a counselor-led group discussion: (1) encouraging participants to share with the group their life and savings goals, experience with savings, motivations to save, benefits to saving, and long term planning for healthy living; (2) discussing alcohol-free leisure activities and generate motivation to engage in alcohol-free leisure activities; (3) reinforce discrepancy between risky alcohol use and not being engaged in care, not adhering to ART, and long term goals; (4) group "problem solving" about overcoming challenges to reducing alcohol use, including participating in alcohol-free leisure activities, HIV care engagement, and ARV adherence including HIV stigma.

Text message reminders. Intervention arm participants will receive 2 times weekly text message reminders of their goals to increase the salience of delayed rewards of saving money and healthy living. Timing will be approximately 1 hour prior to when the participant reports usually drinking. For confidentiality reasons the text message reminders will not address alcohol, HIV care engagement, or adherence specifically but more broadly focus on "healthy living". We chose the frequency of 2 times weekly based on data showing this frequency is the most acceptable and effective in adherence studies.^{20, 21}

Intervention participation incentives. Based on San Diego State University IRB guidance we will compensate participants specifically for the time involved in participation since participation may require them to take time away from work. The intervention arm involves significantly more time commitment (approximately 563 minutes) than the control arm (approximately 195 minutes) and participants will be compensated accordingly. The per hour rate (18,000 Shillings, ~ \$5) will be equivalent between study arms. We detail participant incentives below:

Control group: Alcohol screening and referral. Control condition participants will complete the baseline questionnaire, which includes the AUDIT-C screening for risky alcohol use. After completing their baseline assessment, enhanced control condition participants will receive very brief feedback on their AUDIT-C score according to the feedback suggested in the AUDIT brief intervention manual,²² be provided a referral for alcohol counseling, and briefly engaged in discussion of the importance of HIV care engagement and adherence according to the MOH protocol.²³ The control session will last approximately 20 minutes. The control is an enhanced treatment as usual arm which is recommended for feasibility and preliminary efficacy studies.²⁴

Sample size for randomized pilot intervention trial

We will conduct a stage 1b pilot randomized controlled trial of the intervention. As a pilot study, this study is not powered to detect differences in outcomes, but rather to obtain reliable estimates of effect sizes for a subsequent efficacy trial. However, for illustrative purposes we explore power assuming a small effect size ($d= 0.2$) which is consistent with most brief MI-based alcohol intervention study effect sizes^{17, 25-27} as well as care engagement interventions.²⁸⁻³² **We plan to enroll 160 participants in the pilot intervention trial** with 80 in each arm i.e., randomizing to the KISOBOKA intervention arm (n=80) or to the control arm (n=80, alcohol screening and referral). To be conservative we anticipate 25% attrition. This will provide 72% power to detect an intervention effect and 85% power to detect a study arm x time effect.

Sampling procedure for the randomized pilot intervention trial (n=160).

The participants recruited (based on the inclusion and exclusion criteria) from the Mildmay HIV clinics in Wakiso District will be requested to share the research assistant's contact details (phone numbers) with their potentially eligible friends. This snowball-sampling procedure will enable us to reach more participants in this hard-to-reach population. Those interested in participating in the study will contact the research assistant who will then take them through subsequent eligibility screening and recruitment procedures. This process will be repeated until the required sample is attained.

Randomization for stage 1b randomized pilot intervention trial.

Individual-level randomization with permuted block assignment balancing 1:1 will be used to create equal size groups for the two study arms. Blocks of 8 or 10 study-generated ID numbers will be created and randomly assigned to intervention or control. Once a participant is screened as eligible and attends an enrollment/baseline visit they will be assigned a study-generated ID number from the pre-randomized list which determined their study arm assignment.

Study variables

Dependent variables

Primary outcomes:

- Phosphatidylethanol (PEth) (alcohol biomarker, blood sample)
- AUDIT-C score¹⁹
- ART adherence³³

Secondary outcomes:

- HIV care engagement
- HIV viral load obtained from clinic records
- Frequency of heavy/binge drinking

Potential covariates

- Receipt of instrumental and emotional social support³⁴
- Dimensions of HIV stigma:³⁵ (a) anticipated stigma³⁶; (b) enacted stigma³⁶; and (c) internalized stigma³⁷
- Delay discounting³⁸
- Motivation for HIV care engagement³⁹
- Income and food insecurity⁴⁰
- HIV status disclosure^{28, 34}
- Depressive symptoms⁴¹
- Subjective health status using the MOS-HIV short form⁴²
- Distance/time to the clinic⁴³

